5.3. Exploratory Objectives

- To evaluate the accuracy of an investigational wearable watch device from Empatica in recording seizure counts.
- To evaluate the performance of an investigational electronic seizure diary in the form of a smartphone application (Empatica MATE).

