Seizure history at screening will be derived from the HEP. The subject will be asked about the number and types of seizures that occurred for the longest available period up to 3 months prior to screening. These data will be recorded by the Investigator on a separate seizure history case report form.

During the study, the number of seizures by type will be obtained from subject entries in a standard paper diary and an electronic seizure diary daily starting at Visit 1 and up to Visit 9 (EOS, the end of the 24-week Maintenance Phase). The diaries require an entry every day whether a seizure occurs or not. Subjects will record information for each seizure by date and type of seizure. A full description of the use of the seizure diaries is provided in [Section 11.2.2.4](#).

The subject will also be issued an investigational wearable seizure detection device at Visit 1 to collect exploratory data evaluating the identification of seizure activity based on skin conduction. The subject will wear the watch throughout the duration of the study, up to Visit 9. Additional details are available in [Section 11.2.3](#).

Eligible subjects will begin the 2-week Titration Phase on Day 1 (Week 1), during which they will initiate treatment with ESL 400 mg/day and remain on that dose for 1 week (Days 1 - 7). Subjects will titrate to ESL 800 mg/day the beginning of week 2 (Day 8) and will remain on that dose for 1 week up to the beginning of the maintenance phase. Subjects will maintain a minimum dose of 800 mg/day for the Maintenance Phase; however, during the Maintenance Phase, subjects may titrate in weekly increments of 400 mg/day as medically indicated at the discretion of the Investigator up to a maximum dose of 1200 mg/day (Canadian sites) or 1600 mg/day (US sites) (based on maximum local labelled dose). Additional details are provided in [Section 10.1.1](#).

Subjects who complete the 24-week Maintenance Phase may choose to continue treatment with commercial ESL. Subjects who chose not to continue treatment with ESL at the end of the Maintenance Phase will be gradually tapered off drug provided that they do not have an AE that requires abrupt discontinuation of the study drug.

Subjects who prematurely discontinue treatment with ESL for any reason will be gradually tapered off study drug. However, abrupt discontinuation of the drug is permitted for the treatment of an AE. Subjects who prematurely discontinue treatment with ESL will be withdrawn from the study.

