7.2. Handling of Dropouts or Missing data

Subjects who dropped out before study completion are not to be replaced and all available information obtained from them will be included in the appropriate efficacy and safety summaries to the time of dropout. No imputation is planned for any safety measures.

If the date of the seizure is missing or incomplete and the seizure cannot be allocated to a study interval, these data will not be used in the analysis, but will be presented in the subject data listings. If the seizure diary was returned and there was no seizure data available for a day during that evaluation period, it will be assumed that the patient had missing seizure data, and the day will be excluded from the calculation of the standardized seizure frequency.

Seizure related variables will be calculated based on available data. For dropout subjects, their seizure frequency will be derived for each interval up to the last interval where the subject had data. The last interval standardized seizure frequency (SSF) will be computed based on available data prior to dropout.

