15.2. Efficacy Variables

15.2.1. Efficacy Variables and Derivation

The following periods (days) are used in the efficacy analyses:

- Baseline: the duration (months) recorded for the number of seizure prior to screening from seizure history plus the days from screening to first dose of study medication via the paper seizure diary.
- Titration: date of Visit 3 (week 3) - Visit 2 (week 1)
- Each visit intervals between Visit 3 (week 3) and Visit 9 (week 27): Visit 3 to Visit 4, Visit 4 to Visit 5, Visit 5 to Visit 6, Visit 6 to Visit 7, Visit 7 to Visit 8, and Visit 8 to Visit 9
- First 12 weeks: date of week 15 (Visit 6)- the date of week 3 (Visit 3)
- Last 12 weeks: the date of week 27 (Visit 9 (EOS))- the date of week 15
- 24 weeks of the Maintenance Phase: date of week 27 (Visit 9 (EOS)) – date of week 3 (Visit 3)

For dropout subjects, if subject withdrew before the scheduled Visit 9(EOS), seizure data will be included for each interval up to the last date where the subject had data.

Seizure related efficacy endpoints will be derived based on the paper seizure diary data. Standard Seizure Frequency (SSF)

Seizure frequency from the subject's seizure diary data will be evaluated by standardizing the sum of seizures to a frequency per 4 weeks (28 days).

The standardized seizure frequency (SSF) for any given period (including baseline) will be calculated as:

$$\frac{\text{Total number of seizures reported in the diary during the interval of interest}}{\text{Number of days for the interval of interest}} \times 28 \text{ days}$$

The number of days on study for the interval of interest will be determined by:

Visit Date of last visit during the interval of interest - Visit Date of first visit during the interval of interest. Subject with missing paper seizure data in the interval of interest will not be counted toward the denominator.

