15.4. Exploratory Variables

15.4.1. Analysis of Exploratory Variables

The exploratory analyses will be performed for the mITT populations.

The proportions of concordance in the daily seizure frequency during the 24-weeks of the Maintenance Phase between the watch device and paper diary as well as between the Mate application and paper seizure diary for each subject will be calculated. Proportion is calculated as the number of days with concordance in daily seizure frequency between the two Empatica devices and paper seizure diary divided by the number of days with seizure frequency available in paper diary. The mean and 95% CI (exact method) of the proportion of the concordance will be provided.

In addition, the proportion of concordance in daily seizure frequency during the 24-weeks of the Maintenance Phase between the Mate application and paper seizure diary will be calculated only with the subjects who confirmed they reported all their seizures at each day (i.e. seizure compliance='Y') in the Mate application.

SSF will be calculated for the first 12 weeks, the last 12 weeks, and the 24 weeks of the Maintenance Phase using the seizure data recorded by the investigational wearable watch device, and MATE application from Empatica.

The concordance correlation coefficient (CCC)¹ with 95% confidence interval will be calculated to assess agreement in SSF during the first 12 weeks, the last 12 weeks, and the 24 weeks of the Maintenance Phase between the two Empatica devices and the paper seizure diary.

The concordance correlation coefficient, r_c , for measuring agreement between continuous variables X and Y (both approximately normally distributed), is calculated as follows:

$$r_c = \frac{2S_{XY}}{S_{XX} + S_{YY} + (\bar{X} - \bar{Y})^2}$$

where S_{XX} = variance of X, S_{YY} = variance of Y, S_{XY} = covariance of X and Y.

This is a measure of how well a set of data (Y) compares to a “gold standard” measurement or test (X). It measures both the precision (similar to Pearson’s correlation coefficient), and accuracy (i.e. how far away results are from a 45-degree line through the origin, or from perfect concordance) of the association.

. Similar to the other correlation coefficient, the concordance correlation satisfies $-1 \leq rc \leq +1$. A value of $rc = +1$ corresponds to perfect agreement. A value of $rc = -1$ corresponds to perfect negative agreement, and a value of $rc = 0$ corresponds to no agreement.

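### Watch concordance is divided by paper-diary days with no rule for days without watch data, so the accuracy estimate depends on wear time

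*SAP*

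**What the plan says.** Protocol 5.3 sets the watch objective: "To evaluate the accuracy of an investigational wearable watch device from Empatica in recording seizure counts". For the Mate app, the objective is the performance of an electronic seizure diary.

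SAP 15.4.1 plans, per subject, "The proportions of concordance in the daily seizure frequency during the 24-weeks of the Maintenance Phase between the watch device and paper diary", and the same for the app. The numerator is the count of days on which device and diary agree. The denominator is given by the words "divided by the number of days with seizure frequency available in paper diary". No condition is placed on device data. The analysis set is mITT, which under SAP 5.2 needs only paper seizure data beyond membership of the safety population. Protocol 15.3.9 names the same proportion without giving a denominator.

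On wear, Protocol 7.1 says: "The subject will wear the watch throughout the duration of the study, up to Visit 9". Neither document gives a minimum wear time, a definition of a valid watch day, or a summary of coverage.

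For the paper diary there is a missing-day rule. SAP 7.2 says that when a returned diary has no seizure data for a day, "the day will be excluded from the calculation of the standardized seizure frequency". No parallel rule is written for watch days. For the app, SAP 15.4.1 adds a further concordance analysis "only with the subjects who confirmed they reported all their seizures at each day (i.e. seizure compliance='Y') in the Mate application". The watch has no counterpart.

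SAP 15.4.1 also computes a standardized seizure frequency (SSF) from each device and compares it with the paper SSF by a concordance correlation coefficient (CCC). It gives no day count for the device SSF. The only day count written is in SAP 15.2.1, "Visit Date of last visit during the interval of interest - Visit Date of first visit during the interval of interest", and the formula there is for seizures reported in the diary.

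**The concern.** A day with a diary entry but no watch data (not worn, not charged, not synced) stays in the denominator. If an empty day is not a count, it can never be concordant. If it is read as zero, it is concordant on every day the diary records no seizure. The SAP does not choose between these. Either way the result moves with wear time, and the choice between them is left to programming. A subject who never wore the watch still qualifies for the watch analysis, because mITT depends on paper data only.

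A low figure could mean a poor detector or a watch left in a drawer. A high figure could come largely from days on which the watch recorded nothing. Neither can be read as the accuracy that the objective asks for.

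**Working it through.** The plan states no expected concordance, so there is no figure to reproduce. The check is direct arithmetic on the definition.

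**Inputs**
- Period: 24 weeks × 7 = 168 days (SAP 15.4.1).
- w, the share of diary days with watch data: assumed 0.9, 0.7, 0.5 and 0.
- a, the agreement on days with watch data: assumed 0.95, with 0.80 as a second case.
- s, the share of days with a seizure. The lowest value is the entry minimum in Protocol 8.1, 3 seizures in six months. With the SAP 6.3 month of 30.42 days and each seizure on its own day, s = 3/(6 × 30.42) = 0.0164. The other two values are assumed: 4/28 = 0.143 and 8/28 = 0.286.
- s is taken to be the same on worn and unworn days.

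**Formulas**
- Paper-day denominator, empty day discordant: w × a.
- Paper-day denominator, empty day read as zero: w × a + (1 − w) × (1 − s).
- Denominator restricted to days with both sources: a, for any w above 0.

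**Worked case, w = 0.7, a = 0.95.** Empty days: 0.3 × 168 = 50.4 per subject.
- Discordant: 0.7 × 0.95 = 0.665.
- Zero, s = 0.0164: 0.665 + 0.3 × 0.9836 = 0.960.
- Zero, s = 0.286: 0.665 + 0.3 × 0.714 = 0.879.

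**Results, a = 0.95**

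| Wear share w | Empty = discordant | Empty = zero, s = 0.0164 | s = 0.143 | s = 0.286 | Both sources |
|---|---|---|---|---|---|
| 0.9 | 0.855 | 0.953 | 0.941 | 0.926 | 0.950 |
| 0.7 | 0.665 | 0.960 | 0.922 | 0.879 | 0.950 |
| 0.5 | 0.475 | 0.967 | 0.904 | 0.832 | 0.950 |
| 0 | 0.000 | 0.984 | 0.857 | 0.714 | not defined |

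The gap between the two codings is (1 − w) × (1 − s). Over this range of s it is 7.1 to 9.8 points at 90% wear, 21.4 to 29.5 at 70%, and 35.7 to 49.2 at 50%.

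**Weaker watch, a = 0.80, w = 0.5.** Discordant: 0.400. Zero: 0.892, 0.829 and 0.757 for the three values of s. At the two lower seizure rates, half the days unworn makes this watch look better than its true 0.80.

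**The case against.** The best defence is that the paper-day denominator is a legitimate as-used measure. The diary is the comparator, subjects are told to wear the watch throughout, and the study is framed as real-world. Counting a non-wear day as a failure then answers a sensible question. That stands as a reason to keep the measure, but not as the only one: the stated objective is accuracy, and the as-used reading still needs a written rule that empty days are discordant.

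The app is in a different position. A reader might infer that its concordance has the same defect. The documents do not support putting it that strongly. The app's objective is performance, under which a missed entry may properly count against it, and the additional compliance-restricted analysis partly deals with incomplete reporting. The main app proportion does still use paper days only.

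The size rests on assumed wear and agreement. No document gives either, and at 90% wear the gap between codings is below 10 points. This is why a range is shown.

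A reader might also infer that a both-sources denominator turns daily concordance into a clean measure of accuracy. It does not. A watch worn every day that detects nothing would still agree on every seizure-free day and score 1 − s, that is 71.4% to 98.4% here. The change removes the dependence on wear, not the dominance of days on which both sources read zero.

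Finally, Protocol 11.2.3 refers to a study manual for watch details, and a valid-day rule may sit there. That manual is not among the documents, and SAP 15.4.1 does not point to it.

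**Conclusion.** The concern holds for the watch's daily concordance. Followed as written, the definition keeps days and subjects without watch data in the denominator and leaves their scoring open. With 95% agreement on worn days and wear between 50% and 90%, the reported figure could lie anywhere from 47.5% to 96.7%. These values rest on assumed wear, agreement and seizure-day share; the dependence on wear follows from the definition itself.

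One might infer that the device SSF has the same fault, because SAP 15.2.1 counts days by visit dates, and that non-wear therefore caps the CCC. The documents do not establish this. The SAP 15.2.1 formula is written for diary seizures, SAP 15.4.1 gives no day count for device SSF, and the SAP 7.2 exclusion of days without data could equally be carried over. Nor would there be one cap. Suppose the visit span were used, and every subject had the same wear share and lost exactly that share of seizures. The CCC of a watch that is perfect while worn would be 2w/(1 + w² + (1 − w)²/CV²), where CV is the between-subject SD of SSF divided by its mean. At w = 0.7 this is 0.757, 0.886 and 0.926 for CV 0.5, 1 and 2. The supportable statement is that the device SSF day count is unspecified.

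The analysis is exploratory and descriptive. It has no bearing on the retention endpoint or on the diary-based efficacy endpoints. It is still worth correcting, because as written it cannot answer the objective that it serves.

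**What to change.** - **Watch, main analysis:** define a day with watch data available, and use as denominator the days with both paper-diary data and watch data.
- **Coverage:** report watch days divided by diary days separately, by arm.
- **Watch, sensitivity analysis:** keep the paper-day denominator as an as-used measure, stating that empty days count as not concordant.
- **App:** keep the compliance-restricted analysis, and report the both-sources version beside the paper-day version.
- **SSF and CCC:** compute device SSF per 28 days of device data, and compute the paper SSF used in the CCC over the same days.

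The cost is SAP wording and programming, settled before database lock, and fewer analysed days. It also needs a flag for device data available on each day. The documents do not show that such a flag was collected, so this should be confirmed first. If it cannot be derived, the report should say that concordance reflects wear as well as accuracy and state how empty days were scored.

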11.2.3. Empatica Watch

This study will use the Embrace watch produced by Empatica. Embrace measures physiological data (3-axis accelerometer and gyro, skin conductance, skin temperature), runs pattern analysis, and issues alerts. The watch is designed such that subjects are not aware what data are collected/measured while they are wearing the watch.

The subject should wear the watch on the same arm throughout the study. The watch should be worn on the same side of the body as the subject's seizure focus (side of brain), if known.

For additional details, refer to the study manual.

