15.3.9. Exploratory Analyses

The proportions of concordance in the daily seizure frequency during the 24-weeks of the Maintenance Phase between the watch device and paper diary as well as between the Mate application and paper diary for each subject will be calculated.

SSF during the first 12 weeks, the last 12 weeks, and the 24 weeks of the Maintenance Phase will be calculated using the seizure data recorded by the investigational wearable watch device, and MATE application from Empatica. The concordance correlation coefficient (CCC) with 95% confidence interval will be calculated to assess agreement in SSF during the first 12 weeks, the last 12 weeks, and the 24 weeks of the Maintenance Phase between the two Empatica devices and the paper diary.

Scatter plots of the above SSFs using the seizure data recorded by the watch device as well as Mate application by those from the paper diary will be presented to evaluate agreement graphically.

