3.1. General Description

This is a 31-week, multicenter, 2-arm, prospective, open-label, non-randomized, Phase 4 study of ESL as adjunctive therapy in adult subjects with a diagnosis of epilepsy with POS. Two groups of ESL-naïve subjects will be evaluated. The groups are defined as follows:

Arm 1 (ESL as first add-on): This group will include subjects who have been maintained on a regimen consisting of a stable dose of LEV or LTG for at least 1 month (28 days) prior to screening and who have not used any adjunctive treatment.

Arm 2 (ESL as later add-on): This group will include subjects who have been maintained on a regimen consisting of a stable dose of 1 - 2 anti-epileptic drugs (AEDs) (excluding oxcarbazepine [OXC]) for at least 1 month (28 days) prior to screening and who have used adjunctive treatment in the past.

The Arm 1 subjects will allow an assessment of the efficacy and safety of ESL in subjects who are early in the course of their disease and being treated with one of the most common first line AEDs. The subjects in Arm 2 are similar to the subject population in the Phase 3 adjunctive studies, treatment-resistant subjects who are later in the course of their disease. The inclusion of these subjects in the present study will provide an assessment of the efficacy and safety of ESL as a later adjunctive therapy in a real world clinical setting. In addition, this study will provide data from both Arm 1 and Arm 2 for several behavioral, mood-related, and QOL-related assessments that were not evaluated in the Phase 3 program.

Approximately 100 subjects will be enrolled (approximately 50 subjects in Arm 1 and 50 subjects in Arm 2).

The study will consist of a Screening Phase of 1 to 2 weeks, followed by a 2-week Titration Phase, a 24-week Maintenance Phase, and a Safety Follow-up/Taper Phase of 4 weeks. The last visit in the Maintenance Phase (Visit 9) is considered the End of Study (EOS) visit.

The screening visit should take place 7 - 10 days prior to the titration visit and may be extended to 7 - 17 days if required with consent of medical monitor. Subjects of Asian ancestry who require HLA-B*1502 testing (eg do not have prior test results) may have the screening visit 7 - 17 days prior to the titration visit.

Subjects who withdraw prior to the EOS visit should have an Early Discontinuation Visit (EDV) within 72 hours.

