15.1.2. Primary Analysis of Primary Outcome Variable

The primary analysis will be performed for the safety population.

The number and proportion (%) of subjects completing the 24 weeks of the Maintenance Phase will be provided along with a 95% confidence interval using the exact method.

It will be also summarized by age group, race group, gender, baseline AEDs and number of baseline AEDs.

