Scatter plots of the above SSFs using the seizure data recorded by the watch device as well as Mate application and by those from the paper seizure diary will be presented to evaluate agreement graphically.

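### The exact confidence interval planned for mean device–diary concordance does not fit a mean of per-subject proportions

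*SAP*

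**What the plan says.** Protocol section 15.3.9 asks for daily concordance over the 24-week Maintenance Phase between the watch and the paper diary, "as well as between the Mate application and paper diary for each subject will be calculated". It specifies neither a mean across subjects nor an interval for these proportions.

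SAP section 15.4.1 repeats the per-subject calculation ("as well as between the Mate application and paper seizure diary for each subject will be calculated"). It defines each proportion as the number of concordant days "divided by the number of days with seizure frequency available in paper diary", and adds: "The mean and 95% CI (exact method) of the proportion of the concordance will be provided". No n is given for that interval and the method is not named further.

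The same term appears in three other places. In SAP section 15.1.2 the completion proportion "will be provided along with a 95% confidence interval using the exact method". Sections 15.2.2.3 (responder rates) and 15.2.2.5 (seizure freedom) use it in the same way. In all three, each subject contributes a single yes or no.

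**The concern.** An exact binomial interval needs a count of successes out of a fixed number of independent trials. That holds for completion, response and seizure freedom. It does not hold for the average of about 50 fractions per arm, each with its own denominator of diary days.

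The programmer would have to choose an n. Treating every subject-day as an independent trial ignores that days from one subject resemble each other. Using the number of subjects treats each subject's fraction as if it were one yes/no outcome, which has far more variance than an average over many days. The first choice overstates the precision of the device result and the second understates it. Device accuracy is a stated exploratory objective (SAP section 2.3), and this interval would be printed beside its main daily figure.

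**Working it through.** The documents give no interval width, mean concordance or between-subject variation for this analysis, so there is no planned figure to reproduce. The check compares candidate intervals under stated assumptions.

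**Inputs from the documents**
- About 50 subjects per arm (SAP section 3.1: "Approximately 100 subjects will be enrolled (approximately 50 subjects in Arm 1 and 50 subjects in Arm 2").
- A 24-week Maintenance Phase, so at most 24 × 7 = 168 days per subject and 50 × 168 = 8,400 subject-days per arm.

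**Assumptions**
- Mean concordance m = 0.95.
- Subject-level concordance follows a beta distribution, with days independent given the subject's own value.
- ICC ρ of 0, 0.02, 0.05, 0.10 or 0.20. The between-subject SD is √(ρ × 0.95 × 0.05), which is 3.1 points at ρ = 0.02 and 9.7 points at ρ = 0.20.

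**Pooled subject-days**

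The half-width is about 1.96 × √(0.95 × 0.05 / 8,400) = 0.0047, or 0.47 points, whatever ρ is. The true variance of the mean is larger by the design effect 1 + 167ρ, so approximate coverage is 2Φ(1.96 / √(1 + 167ρ)) − 1:

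| ρ | 1 + 167ρ | 1.96 / √(1 + 167ρ) | Coverage, formula | Coverage, simulated |
|---|---|---|---|---|
| 0 | 1 | 1.96 | 95% | 95% |
| 0.02 | 4.34 | 0.941 | 65% | 67% |
| 0.05 | 9.35 | 0.641 | 48% | 48% |
| 0.10 | 17.7 | 0.466 | 36% | 36% |
| 0.20 | 34.4 | 0.334 | 26% | 27% |

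The formula does not contain the number of subjects, so the protocol's 93 and 97 per arm would give the same coverage. If half the subjects leave and contribute an assumed 84 days each, simulated coverage at ρ = 0.02 to 0.20 is 69%, 51%, 38% and 28%.

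**n = number of subjects**

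0.95 × 50 = 47.5, so the count rounds to about 47 or 48. The exact limits are 83.5% to 98.7% for 47 of 50 and 86.3% to 99.5% for 48 of 50. The half-widths are 7.6 and 6.6 points, averaging about 7.1. Simulated coverage is 100%.

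**Subject-level t-interval**

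Mean simulated half-widths at ρ = 0.02, 0.05, 0.10 and 0.20 are 1.0, 1.4, 2.0 and 2.7 points. Coverage falls from about 95% to 91% across that range. The pooled interval is therefore 2.1 to 5.8 times too narrow (0.99 / 0.47 to 2.71 / 0.47). The n = 50 interval is about 7 to 2.6 times too wide (7.1 / 1.0 to 7.1 / 2.7).

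**Other assumptions**

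With mean concordance of 0.70 to 0.90, between-subject SD of 5 to 20 points and 50 subjects, pooled coverage runs from 75% down to 19%. The t-interval covers 92.5% to 95.0%. At mean 0.80 and SD 15 points, the full widths are 1.7 points pooled (coverage 30%), 23.6 points with n = 50 (coverage 100%) and 8.6 points for the t-interval (coverage 94%). The pattern does not depend on the 95% scenario.

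**The case against.** **The binomial reading is an inference.** Section 15.4.1 says only that the method is exact. SAP section 8 refers to output templates supplied with the SAP; they are not among the documents and may show an n. This stands as a caution about wording. But every other use of the term in the SAP is for a binary outcome per subject, no exact method for a mean is named, and no choice of n makes a binomial interval fit a mean of fractions with differing denominators.

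**A reader might infer that the interval fails in the same way under either n.** The figures do not support that. Pooling is correct when concordance does not vary between subjects, although that is unlikely when seizure rates differ. With n equal to the number of subjects the interval is conservative: it wastes precision but does not claim too much.

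**The sizes rest on assumptions.** This stands: the mean, the ICCs and the beta model are not in the documents. The direction of each error does not depend on the exact values.

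**The replacement is imperfect.** This also stands. With concordance near 100% and strong between-subject variation, a t-interval covers somewhat less than 95%. Its upper limit can also pass 100%: in about 16% of simulated runs at an ICC of 0.47, and essentially none at 0.20 or below.

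**A reader might go further and infer that the concordance measure itself is faulty**, because seizure-free days dominate it and section 15.4.1 gives no rule for diary days without device data. The documents do not show an error there. The objective concerns seizure counts. The concordance correlation coefficient addresses counts, and so do the scatter plots, which "will be presented to evaluate agreement graphically". A second MATE analysis is limited to subjects who confirmed full reporting. Handling of watch data may be covered elsewhere (protocol section 11.2.3: "For additional details, refer to the study manual").

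**Conclusion.** The sentence is wrong as written if exact means exact binomial, which is the only reading the rest of the SAP supports. Under the assumed 95% mean, 50 subjects and 168 days, pooling days covers about 67% at an ICC of 0.02 and 27% at 0.20, and is right only at zero. Taking n as the number of subjects gives a half-width of about 7 points where 1.0 to 2.7 would do.

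The point is minor. The analysis is exploratory and SAP section 6.6 plans no testing. The per-subject proportions, the concordance correlation coefficient and the scatter plots do not depend on this interval. Nothing here bears on the retention, seizure or safety results, and the exact intervals for completion, response and seizure freedom are appropriate.

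**What to change.** In the sentence on the mean in SAP section 15.4.1, replace the exact method with a 95% subject-level bootstrap or t-interval for the mean of the per-subject proportions, reported by arm, with limits truncated at 100%. Apply the same interval to the MATE analysis restricted to confirmed reporters, if an interval is given there. Leave all other planned device outputs as they are.

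The cost is one phrase in the SAP and a small programming change, with no new data. The downside is that coverage can fall slightly below 95% when concordance is near 100% and varies strongly between subjects.
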